5.4 Stratification

Since this is a single arm Phase II study, enrollment will not be stratified.

5.5 Concomitant Medications/Vaccinations (allowed & prohibited)

Medications or vaccinations specifically prohibited in the exclusion criteria are not allowed during the ongoing trial. If there is a clinical indication for one of these or other medications or vaccinations specifically prohibited during the trial, discontinuation from trial therapy or vaccination may be required. The investigator should discuss any questions regarding this with the Merck Clinical team. The final decision on any supportive therapy or vaccination rests with the investigator and/or the subject's primary physician.

5.5.1 Acceptable Concomitant Medications

All treatments that the investigator considers necessary for a subject's welfare may be administered at the discretion of the investigator in keeping with the community standards of medical care. All concomitant medication will be recorded on the case report form (CRF) including all prescription, over-the-counter (OTC), herbal supplements, and IV medications

and fluids. If changes occur during the trial period, documentation of drug dosage, frequency, route, and date may also be included on the CRF.

All concomitant medications received within 28 days before the first dose of trial treatment and 30 days after the last dose of trial treatment should be recorded. Concomitant medications administered after 30 days after the last dose of trial treatment should be recorded for SAEs and ECIs as defined in Section 6.3.

5.5.2 Prohibited Concomitant Medications

Subjects are prohibited from receiving the following therapies during the Screening and Treatment Phase (including retreatment for post-complete response relapse) of this trial:

- Antineoplastic systemic chemotherapy or biological therapy
- Immunotherapy not specified in this protocol
- Chemotherapy not specified in this protocol
- Investigational agents other than pembrolizumab
- Radiation therapy
 - Note: Radiation therapy to a symptomatic solitary lesion or to the brain may be allowed at the investigator's discretion.
- Live vaccines within 30 days prior to the first dose of trial treatment and while participating in the trial. Examples of live vaccines include, but are not limited to, the following: measles, mumps, rubella, varicella/zoster, yellow fever, rabies, BCG, and typhoid vaccine.
- Systemic glucocorticoids for any purpose other than to modulate symptoms from an event of clinical interest of suspected immunologic etiology. The use of physiologic doses of corticosteroids may be approved after consultation with the Sponsor.

Subjects who, in the assessment by the investigator, require the use of any of the aforementioned treatments for clinical management should be removed from the trial. Subjects may receive other medications that the investigator deems to be medically necessary.

The Exclusion Criteria describes other medications which are prohibited in this trial.

There are no prohibited therapies during the Post-Treatment Follow-up Phase.

5.6 Rescue Medications & Supportive Care

5.6.1 Supportive Care Guidelines

Subjects should receive appropriate supportive care measures as deemed necessary by the treating investigator. Suggested supportive care measures for the management of adverse events with potential immunologic etiology are outlined below. Where appropriate, these

measures may include the use of oral or intravenous treatment with corticosteroids as well as additional anti-inflammatory agents if symptoms do not improve with administration of corticosteroids. Note that several courses of steroid tapering may be necessary as symptoms may worsen when the steroid dose is decreased. For each disorder, attempts should be made to rule out other causes such as metastatic disease or bacterial or viral infection, which might require additional supportive care. The treatment guidelines are intended to be applied when the investigator determines the events to be related to pembrolizumab.

Note: if after the evaluation the event is determined not to be related, the investigator is instructed to follow the ECI reporting guidance detailed in Section 6.3.3.2, but does not need to follow the treatment guidance. Refer to Section 5.2.1 for dose modification.

It may be necessary to perform conditional procedures such as bronchoscopy, endoscopy, or skin photography as part of evaluation of the event.

- **Pneumonitis:**

- For **Grade 2 events**, treat with systemic corticosteroids. When symptoms improve to Grade 1 or less, steroid taper should be started and continued over no less than 4 weeks.
- For **Grade 3-4 events**, immediately treat with intravenous steroids. Administer additional anti-inflammatory measures, as needed.
- Add prophylactic antibiotics for opportunistic infections in the case of prolonged steroid administration.

- **Diarrhea/Colitis:**

Subjects should be carefully monitored for signs and symptoms of enterocolitis (such as diarrhea, abdominal pain, blood or mucus in stool, with or without fever) and of bowel perforation (such as peritoneal signs and ileus).

- All subjects who experience diarrhea/colitis should be advised to drink liberal quantities of clear fluids. If sufficient oral fluid intake is not feasible, fluid and electrolytes should be substituted via IV infusion. For Grade 2 or higher diarrhea, consider GI consultation and endoscopy to confirm or rule out colitis.
- For **Grade 2 diarrhea/colitis** that persists greater than 3 days, administer oral corticosteroids.
- For **Grade 3 or 4 diarrhea/colitis** that persists > 1 week, treat with intravenous steroids followed by high dose oral steroids.
- When symptoms improve to Grade 1 or less, steroid taper should be started and continued over no less than 4 weeks.

- **Type 1 diabetes mellitus (if new onset, including diabetic ketoacidosis [DKA]) or \geq Grade 3 Hyperglycemia, if associated with ketosis (ketonuria) or metabolic acidosis (DKA)**

- For **T1DM** or **Grade 3-4 Hyperglycemia**

- Insulin replacement therapy is recommended for Type I diabetes mellitus and for Grade 3-4 hyperglycemia associated with metabolic acidosis or ketonuria.
- Evaluate patients with serum glucose and a metabolic panel, urine ketones, glycosylated hemoglobin, and C-peptide.

- **Hypophysitis:**

- For **Grade 2** events, treat with corticosteroids. When symptoms improve to Grade 1 or less, steroid taper should be started and continued over no less than 4 weeks. Replacement of appropriate hormones may be required as the steroid dose is tapered.
- For **Grade 3-4** events, treat with an initial dose of IV corticosteroids followed by oral corticosteroids. When symptoms improve to Grade 1 or less, steroid taper should be started and continued over no less than 4 weeks. Replacement of appropriate hormones may be required as the steroid dose is tapered.

- **Hyperthyroidism or Hypothyroidism:**

Thyroid disorders can occur at any time during treatment. Monitor patients for changes in thyroid function (at the start of treatment, periodically during treatment, and as indicated based on clinical evaluation) and for clinical signs and symptoms of thyroid disorders.

- **Grade 2** hyperthyroidism events (and **Grade 2-4** hypothyroidism):
 - In hyperthyroidism, non-selective beta-blockers (e.g. propranolol) are suggested as initial therapy.
 - In hypothyroidism, thyroid hormone replacement therapy, with levothyroxine or liothyroinine, is indicated per standard of care.
- **Grade 3-4** hyperthyroidism
 - Treat with an initial dose of IV corticosteroid followed by oral corticosteroids. When symptoms improve to Grade 1 or less, steroid taper should be started and continued over no less than 4 weeks. Replacement of appropriate hormones may be required as the steroid dose is tapered.

- **Hepatic:**

- For **Grade 2** events, monitor liver function tests more frequently until returned to baseline values (consider weekly).
 - Treat with IV or oral corticosteroids
- For **Grade 3-4** events, treat with intravenous corticosteroids for 24 to 48 hours.
- When symptoms improve to Grade 1 or less, a steroid taper should be started and continued over no less than 4 weeks.

- **Renal Failure or Nephritis:**

- For **Grade 2** events, treat with oral corticosteroids.

- For **Grade 3-4** events, treat with systemic (intravenous) corticosteroids.
- When symptoms improve to Grade 1 or less, steroid taper should be started and continued over no less than 4 weeks.

Management of Infusion Reactions: Signs and symptoms usually develop during or shortly after drug infusion and generally resolve completely within 24 hours of completion of infusion.

Table 4 below shows treatment guidelines for subjects who experience an infusion reaction associated with administration of pembrolizumab (MK-3475).

Table 4 Infusion Reaction Treatment Guidelines

NCI CTCAE Grade	Treatment	Premedication at subsequent dosing
Grade 1 Mild reaction; infusion interruption not indicated; intervention not indicated	Increase monitoring of vital signs as medically indicated until the subject is deemed medically stable in the opinion of the investigator.	None
Grade 2 Requires infusion interruption but responds promptly to symptomatic treatment (e.g., antihistamines, NSAIDS, narcotics, IV fluids); prophylactic medications indicated for <=24 hrs	
Stop Infusion and monitor symptoms. Additional appropriate medical therapy may include but is not limited to:
 
 IV fluids Antihistamines NSAIDS Acetaminophen Narcotics 
Increase monitoring of vital signs as medically indicated until the subject is deemed medically stable in the opinion of the investigator. If symptoms resolve within one hour of stopping drug infusion, the infusion may be restarted at 50% of the original infusion rate (e.g., from 100 mL/hr to 50 mL/hr). Otherwise dosing will be held until symptoms resolve and the subject should be premedicated for the next scheduled dose.
 
Subjects who develop Grade 2 toxicity despite adequate premedication should be permanently discontinued from further trial treatment administration.
	
Subject may be premedicated 1.5h (\pm 30 minutes) prior to infusion of pembrolizumab (MK-3475) with:
 
 Diphenhydramine 50 mg po (or equivalent dose of antihistamine). Acetaminophen 500-1000 mg po (or equivalent dose of antipyretic).
Grades 3 or 4 Grade 3: Prolonged (i.e., not rapidly responsive to symptomatic medication and/or brief interruption of infusion); recurrence of symptoms following initial improvement; hospitalization indicated for other clinical sequelae (e.g., renal impairment, pulmonary infiltrates) Grade 4: Life-threatening; pressor or ventilatory support indicated	
Stop Infusion. Additional appropriate medical therapy may include but is not limited to:
 
 IV fluids Antihistamines NSAIDS Acetaminophen Narcotics Oxygen Pressors Corticosteroids Epinephrine 
Increase monitoring of vital signs as medically indicated until the subject is deemed medically stable in the opinion of the investigator. Hospitalization may be indicated.
 
Subject is permanently discontinued from further trial treatment administration.
	No subsequent dosing

NCI CTCAE Grade	Treatment	Premedication at subsequent dosing
Appropriate resuscitation equipment should be available in the room and a physician readily available during the period of drug administration.		

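### Section 5.6.1 suggests steroids later for Grade 3 or 4 diarrhea/colitis (after more than 1 week) than for Grade 2 (after more than 3 days)

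*Combined protocol and SAP*

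**What the plan says.** The Diarrhea/Colitis part of section 5.6.1 gives two steroid triggers, each tied to a grade. For Grade 2 events "that persists greater than 3 days, administer oral corticosteroids". For Grade 3 or 4 events "that persists > 1 week, treat with intravenous steroids followed by high dose oral steroids".

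The same part asks for monitoring for enterocolitis and bowel perforation, for fluids, and, from Grade 2 upward, for GI consultation and endoscopy to be considered. None of these has a waiting period. Table 3 in section 5.2.1.2 holds pembrolizumab at Grade 2-3 diarrhea/colitis and stops it permanently at Grade 4, also without a persistence condition.

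Section 5.6.1 opens by leaving supportive care to the treating investigator and calls the listed measures suggested. Section 5.5.2 prohibits "Systemic glucocorticoids for any purpose other than to modulate symptoms from an event of clinical interest of suspected immunologic etiology", so steroids for a suspected immune-related event are permitted at any time.

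**The concern.** A graded management rule should not become slower as the event becomes more severe. Here it does. A patient who presents at Grade 3 or 4, or who reaches that level before completing 3 days at Grade 2, falls under the bullet with the longer wait.

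Colitis is an immune toxicity of the study drug for which the protocol itself asks sites to watch for perforation. Several sites take part, and this section is their reference for managing such events. A site that follows the bullets literally is pointed to later steroids in the patients with the more dangerous form. The stake is patient safety, not the inference on response rate.

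**Working it through.** There is no stated figure to reproduce. The check is a subtraction and a count of the steroid bullets in section 5.6.1.

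**Gap between the two triggers.** Grade 2: more than 3 days. Grade 3 or 4: more than 1 week, that is, more than 7 days. Difference: 7 - 3 = 4 days, in the wrong direction.

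**Steroid bullets by disorder.**

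| Disorder | Grade 2 steroid bullet | Grade 3-4 steroid bullet | Higher grade later? |
|---|---|---|---|
| Pneumonitis | yes, no wait | "immediately treat with intravenous steroids. Administer additional anti-inflammatory measures, as needed" (no wait) | no |
| Diarrhea/colitis | yes, more than 3 days | yes, more than 7 days | **yes** |
| Hypophysitis | yes, no wait | "treat with an initial dose of IV corticosteroids followed by oral corticosteroids" (no wait) | no |
| Hyperthyroidism | none (beta-blockers) | "Treat with an initial dose of IV corticosteroid followed by oral corticosteroids" (no wait) | not applicable |
| Hepatic | yes, no wait | "treat with intravenous corticosteroids for 24 to 48 hours" (no wait) | no |
| Renal failure/nephritis | yes, no wait | "treat with systemic (intravenous) corticosteroids" (no wait) | no |

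The hepatic 24 to 48 hours is how long treatment lasts, not a delay before it starts. Type 1 diabetes and hyperglycemia are left out because the advice there is insulin. Infusion reactions (Table 4) are left out because steroids appear only as possible additional therapy. That entry has no wait either.

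**Counts.**
- Grade 3-4 steroid bullets: 6, of which 1 has a wait.
- Grade 2 steroid bullets: 5, of which 1 has a wait.
- All grade-specific steroid bullets: 6 + 5 = 11, of which 2 have a wait, both for diarrhea/colitis.
- Disorders with a steroid bullet at both levels: 5, of which 1 has the later trigger at the higher grade.

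**Could another part of the protocol set an earlier trigger?** Sections 5.2.1.2, 5.5.2 and 5.6.1 were read for one. Table 3 governs dosing of pembrolizumab, not steroids. Section 5.5.2 permits steroids but does not say when to start them. The introduction to 5.6.1 allows oral or intravenous steroids where appropriate, in general terms. None replaces the one-week condition.

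**The case against.** The strongest reply is that the protocol already contains the harm. The measures are suggested, the investigator decides, section 5.5.2 allows steroids from the first day, and fluids, the GI work-up and the drug hold or stop all apply at once. This stands as a limit on the consequence. It does not correct the text, because guidance is written to be followed.

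Second, waiting periods seem to be a feature of this disorder's advice, since Grade 2 colitis is also the only Grade 2 event with one. The 1-of-6 count therefore does not prove an error on its own. That is fair. The main evidence is the inversion within the disorder, and the comparison with the other disorders is supporting context.

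Third, the week might be meant for excluding infection, or as an escalation after oral steroids have failed. Section 5.6.1 does ask that other causes, including bacterial or viral infection, be ruled out, but it asks this for every disorder, and a work-up would not explain a longer wait at Grade 3-4 than at Grade 2. The bullet does not mention failure of oral steroids, and its label is Grade 3 or 4, not continuing Grade 2.

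Fourth, a patient already at Grade 2 for more than 3 days has met the oral-steroid trigger before worsening. The text also leaves open whether persistence is counted from onset or from reaching the grade. Both points stand: the 4 days is the difference between two written thresholds, not an expected treatment delay.

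**Conclusion.** The concern holds. As written, the steroid trigger for Grade 3 or 4 diarrhea/colitis is 4 days later than for Grade 2, and no other text supplies an earlier one. This rests on reading the two bullets as grade-specific, which is how they are labelled.

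The consequence is bounded. The documents give no rate of Grade 3-4 colitis, so how many of the 24 patients would be affected cannot be estimated and may be none. The design, power and primary analysis are untouched. It should be corrected because it concerns safety guidance for a known type of toxicity and the correction is easy, not because it threatens the trial's conclusions.

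**What to change.** Ask the sponsor's medical lead to confirm or correct the Grade 3-4 interval. The recommended correction is to delete the one-week persistence condition, so that Grade 3 or 4 diarrhea/colitis goes directly to intravenous and then high-dose oral steroids, in line with the other five Grade 3-4 bullets.

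If the medical lead wants to keep an interval for the infection work-up, it should apply to Grade 3 only and be no longer than the 3 days used at Grade 2. That removes the inversion either way. The documents hold no data that fix the right interval, so the choice is a clinical one.

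The cost is one phrase in the next protocol amendment and a notice to sites. Visits, data collection and analysis do not change.

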5.7 Diet/Activity/Other Considerations

5.7.1 Diet

Subjects should maintain a normal diet unless modifications are required to manage an AE such as diarrhea, nausea or vomiting.

5.7.2 Contraception

Pembrolizumab may have adverse effects on a fetus in utero. Furthermore, it is not known if pembrolizumab has transient adverse effects on the composition of sperm. Non-pregnant, non-breast-feeding women may be enrolled if they are willing to use 2 methods of birth control or are considered highly unlikely to conceive. Highly unlikely to conceive is defined as 1) surgically sterilized, or 2) postmenopausal (a woman who is ≥ 45 years of age and has not had menses for greater than 1 year will be considered postmenopausal), or 3) not heterosexually active for the duration of the study. The two birth control methods can be either two barrier methods or a barrier method plus a hormonal method to prevent pregnancy. Subjects should start using birth control from study Visit 1 throughout the study period up to 120 days after the last dose of study therapy.

The following are considered adequate barrier methods of contraception: diaphragm, condom (by the partner), copper intrauterine device, sponge, or spermicide. Appropriate hormonal contraceptives will include any registered and marketed contraceptive agent that contains an estrogen and/or a progestational agent (including oral, subcutaneous, intrauterine, or intramuscular agents).

Subjects should be informed that taking the study medication may involve unknown risks to the fetus (unborn baby) if pregnancy were to occur during the study. In order to participate in the study they must adhere to the contraception requirement (described above) for the duration of the study and during the follow-up period defined in section 6.3.2-Reporting of Pregnancy and Lactation to the Sponsor and to Merck. If there is any question that a subject will not reliably comply with the requirements for contraception, that subject should not be entered into the study.

5.7.3 Use in Pregnancy

If a subject inadvertently becomes pregnant while on treatment with pembrolizumab, the subject will immediately be removed from the study. The site will contact the subject at least monthly and document the subject's status until the pregnancy has been completed or terminated. The outcome of the pregnancy will be reported to the Sponsor and to Merck without delay and within 24 hours to the Sponsor and within 2 working days to Merck if the

outcome is a serious adverse experience (e.g., death, abortion, congenital anomaly, or other disabling or life-threatening complication to the mother or newborn).

The study investigator will make every effort to obtain permission to follow the outcome of the pregnancy and report the condition of the fetus or newborn to the Sponsor. If a male subject impregnates his female partner the study personnel at the site must be informed immediately and the pregnancy reported to the Sponsor and to Merck and followed as described above and in Section 6.3.2.

5.7.4 Use in Nursing Women

It is unknown whether pembrolizumab is excreted in human milk. Since many drugs are excreted in human milk, and because of the potential for serious adverse reactions in the nursing infant, subjects who are breast-feeding are not eligible for enrollment.

5.8 Subject Withdrawal/Discontinuation Criteria

Subjects may withdraw consent at any time for any reason or be dropped from the trial at the discretion of the investigator should any untoward effect occur. In addition, a subject may be withdrawn by the investigator or the Sponsor if enrollment into the trial is inappropriate, the trial plan is violated, or for administrative and/or other safety reasons. Specific details regarding discontinuation or withdrawal are provided in Section 6– Other Procedures.

A subject must be discontinued from the trial treatment for any of the following reasons:

- The subject or legal representative (such as a parent or legal guardian) withdraws consent.
- Confirmed radiographic disease progression
- Unacceptable adverse experiences as described in Section 5.2.1.2
- Intercurrent illness that prevents further administration of treatment
- Investigator's decision to withdraw the subject
- The subject has a confirmed positive serum pregnancy test
- Noncompliance with trial treatment or procedure requirements
- The subject is lost to follow-up
- Completed 12 months of uninterrupted treatment with pembrolizumab or 17 administrations of study medication, whichever is later.
- *Note: 12 months of study medication is calculated from the date of first dose.*
Administrative reasons

The End of Treatment and Follow-up visit procedures are listed in Section 6 (Protocol Flow Chart) and Section .6.2.5 (Visit Requirements).

From the administration of first treatment until 30 days (unless otherwise specified) subsequent to last treatment or withdrawal of subject, new onset adverse events will be captured. Follow-up and reporting of these events will follow the same procedure as for AEs observed during the study period. Serious Adverse Events will be collected for 90 days after the end of treatment as described in Section 6.3. In addition, any unexpected SAE that occurs more than 90 days after drug administration but is possibly, probably or definitely attributed to drug administration will be recorded and reported.

Subjects who discontinue for reasons other than progressive disease will have post-treatment follow-up for disease status until disease progression, initiating a non-study cancer treatment, withdrawing consent or becoming lost to follow-up. After documented disease progression each subject will be followed by telephone for overall survival until death, withdrawal of consent, or the end of the study, whichever occurs first.

